3 OBJECTIVES AND ENDPOINTS

Table 1. Study Objectives and Endpoints

OBJECTIVES	ENDPOINTS
NDURE FEASIBILITY STUDY	
Primary	
To assess the feasibility of NDURE among white and AA HNSCC patients.	NDURE Accrual Rate NDURE Completion Rate NDURE Session Completion Rate Questionnaire Completion Rate
Secondary	
To assess the acceptability of NDURE to white and AA HNSCC patients and HNSCC providers.	Patient Satisfaction with the Interpersonal Relationship with the Navigator Scale Score Patient Satisfaction with Logistical Aspects of Navigation Scale Score
To determine the feasibility of a single dedicated navigator to manage a caseload of patients for the NDURE intervention	Navigator Caseload Navigator Time Allocation (Direct) Navigator Time Allocation (Indirect)
To evaluate the feasibility of collecting pre- and post-NDURE intervention outcome measures in this patient population	Study questionnaire completion rate
RCT of NDURE VERSUS USUAL CARE	
Primary	
To evaluate the preliminary clinical impact of NDURE compared with UC on delays starting PORT among white and AA HNSCC patients.	PORT Delay Time-to-PORT (TTP) Initiation
Secondary	
To evaluate the preliminary clinical impact of NDURE compared with UC on racial disparities in delays starting PORT among white and AA HNSCC	PORT Delay TTP Initiation

Table 1. Study Objectives and Endpoints

OBJECTIVES	ENDPOINTS
patients.	
To assess the preliminary clinical impact of NDURE compared with UC on barriers to care	Barriers Resolution Rate Unresolved barriers
To determine the preliminary clinical impact of NDURE compared with UC on cancer care delivery processes	Pre-surgical Radiation Consultation Pre-RT Dental Extractions Surgery to Pathology Report \leq 7 d Surgery to PORT Referral \leq 10 d RT Referral to Consult \leq 10 d RT Consult to Initiation \leq 21 d
To evaluate the preliminary behavioral mechanism of action of NDURE	Care Transition Measure-15 (CTM-15) Score Change from Baseline in Interpersonal Support Evaluation List-12 Scale Score Change from Baseline in Perceived Susceptibility Scale Scores Change from Baseline in Illness Perception Questionnaire-Revised (IPQ-R) Consequences Sub-Scale Score Change in Baseline from Perceived Barriers Scale Change in Baseline from Communication & Attitudinal Self-Efficacy Scale (CASE)-Cancer Score

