RT Consult to Initiation <= 21 days is defined as the initiation of PORT within 21 calendar days of the patient being evaluated by a radiation oncologist for PORT.

Health Behavior Constructs

Care Transition Measure-15 (CTM-15) score is reported as a score out of 100 and calculated as the mean score (the summed score from each question divided by the total number of questions) with a linear transformation to 100. The CTM-15 is a validated, psychometrically sound 15-item, unidimensional measure of care transitions across the healthcare system that is consistent with the concept of patient-centeredness and useful from an organization perspective for the purpose of performance measurement and quality improvement⁴⁵. Items are rated on a 4-point Likert scale from 'Strongly Disagree' (1) to 'Strongly Agree' (4). Higher scores reflect more care integration and better care transitions.

Change from baseline in Interpersonal Support Evaluation List-12 (ISEL-12) score is defined as the change in total ISEL-12 scores from baseline. The ISEL-12 is a validated, 12-item assessment of three subscales (appraisal, belonging, and tangible)⁴⁶ that has been used to assess support in prior PN studies⁴⁷. Items are rated on a 4-point Likert scale from 'Definitely False' (1) to 'Definitely True' (4). The score is calculated by summing scores across all items (with reverse coding for items 1, 2, 7, 8, 11, 12). Scores range from 12-48. Higher scores indicate more support.

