9.2.2 RCT OF NDURE VERSUS USUAL CARE

Power and sample size calculations were performed using PASS v08.0.13, “Inequality Tests for Two Independent Proportions.” The primary endpoint for this pilot RCT is the rate of PORT delay, defined as starting PORT > 6 weeks after surgery. Our primary objective is to compare PORT delay rates between the NDURE and usual care arms. We hypothesize that, compared with patients who receive usual care, patients who receive NDURE will have a decreased rate of PORT delay (initiation of PORT > 6 weeks after surgery). Alternatively, our null hypothesis is that there will be no difference in the rate of PORT delay between NDURE and usual care. We assume the rate of PORT delay in the usual care arm will be 45%³³ and target an absolute reduction in PORT delay of 20% (rate of PORT delay in the NDURE arm = 25%)²⁴. This effect size is clinically significant and realistic given results in similar (non-randomized) interventions²⁴. Seventy-five patients in each arm yields 83% power to detect a 20% reduction in PORT delay (45% versus 25%) based on a two-sided Mantel-Haenszel test of two independent proportions assuming a two-sided $\alpha = 0.1$. Our choice of the Mantel-Haenszel test to compare proportions is based on the trial’s stratified design. Our selection of $\alpha = 0.1$ and $1 - \beta = 0.8$ is based on the desire to emphasize power over type I error at this early stage of development (single-site pilot RCT) to ensure follow-up on promising interventions. We therefore consider our RCT to be appropriately and rigorously designed to detect a clinically meaningful reduction in PORT delay. In order to have 150 patients eligible for the

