9.4 STATISTICAL ANALYSES

9.4.1 GENERAL APPROACH

We will construct graphical displays and calculate descriptive statistics (e.g. frequencies and percent for categorical variables, and mean, median, standard deviation, and range for continuous variables). Covariates will be specified below. For inferential tests, we will use a p-value of 0.05, two-sided, and 95% confidence intervals (CIs) to assess statistical significance (Type I error). Covariates will be pre-specified as described below. Normality of the data will be assessed before underlying statistical procedures will be performed. We will evaluate variable transformations as needed to satisfy assumptions and consider transformations of variables to induce approximate normality and stabilize variance as needed. Nonparametric tests will be applied when appropriate.

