9.4.3.2 RCT OF NDURE VERSUS USUAL CARE

We will analyze the secondary endpoint of TTP as a continuous variable and estimate median time to PORT for each arm and for racial subgroups within each arm using Kaplan-Meier curves with Greenwood variance estimation to construct the corresponding 95% CIs. Hazard ratio comparing the two arms will be estimated using Cox proportional hazards regression controlling for the stratification variables. TTP will be compared between intervention arms using a stratified log-rank test on the modified ITT efficacy analysis population.

For the secondary endpoints of barrier reduction and unresolved barriers, we will calculate the proportion of unresolved barriers and the frequency of unresolved barriers (respectively) at the end of NDURE, consistent with prior PN studies⁵¹. We will use logistic regression to assess the relationship between unresolved barriers and the rate of PORT delay (primary endpoint), controlling for covariates listed in **Section 8.1**.

For other secondary endpoints, data will be summarized using frequency and percent for categorical variables and using mean, median, standard deviation, IQR and range for continuous variables. We will construct 95% CIs to provide a measure of uncertainty in estimated proportions and means. Comparisons between trial arms of other secondary endpoints will be performed using *t*-tests and chi-square tests, or Wilcoxon rank sum and Fisher's exact tests as appropriate. Pre- and post-intervention values of variables measuring the theoretical constructs underlying NDURE (i.e. care coordination, self-efficacy in cancer care, support, and knowledge) will be compared using Wilcoxon sign rank tests. Comparisons between arms of the change in scores will be conducted using Wilcoxon rank sum tests. All secondary endpoint

will be analyzed on the modified ITT efficacy analysis population. Missing data will be handled as described in **Section 9.4.2.2, RCT of NDURE Versus Usual Care**.

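### Scales with a baseline score are compared between arms as unadjusted changes by rank-sum test; adjusting for the baseline score would give a more precise estimate at no cost

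*Combined protocol and SAP*

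**What the plan says.** Section 3 sets out the mechanism endpoints of the RCT, most of them as changes, for example "Change from Baseline in Interpersonal Support Evaluation List-12 Scale Score". Section 8.1 confirms that the raw difference is meant: "Change from baseline in Interpersonal Support Evaluation List-12 (ISEL-12) score is defined as the change in total ISEL-12 scores from baseline". Perceived Susceptibility, IPQ-R Consequences and CASE-Cancer are defined in the same way. The CTM-15 is not: "Care Transition Measure-15 (CTM-15) score is reported as a score out of 100".

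The Schedule of Activities (Section 1.3) gives the timing:

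- ISEL-12 and CASE-Cancer: Visits 1 and 5.
- Perceived Susceptibility and IPQ-R Consequences: Visits 1, 3 and 4.
- CTM-15: Visits 3 and 4 only, so it has no baseline.

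Section 4.2.1 places the baseline assessments before randomisation.

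Section 9.4.3.2 gives two analyses for these scales. Pre- and post-intervention values "will be compared using Wilcoxon sign rank tests", and for the arm comparison: "Comparisons between arms of the change in scores will be conducted using Wilcoxon rank sum tests". Neither uses a covariate. Elsewhere the plan does adjust. The primary Mantel-Haenszel test is stratified by race and radiation facility (Section 9.4.2.2), the Cox model and log-rank test for time to PORT use the stratification variables, and the logistic model of PORT delay on unresolved barriers is fitted "controlling for covariates listed in" Section 8.1. Section 9.4.1 promises that covariates will be specified later in the text, but none is named for the change scores.

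**The concern.** A raw change score subtracts the whole baseline value, including its measurement noise, whatever the actual relation between baseline and follow-up. If the arms differ on baseline by chance, regression to the mean moves the changes apart, and the planned test does not correct for that. A model that conditions on baseline estimates the relation from the data and removes the explained part of the variance.

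A rank-sum test also yields a p-value and no effect estimate, whereas Section 4.2.2 wants this pilot to supply precise effect sizes for a definitive trial. Sections 4.2.1 and 4.2.2 further rely on the mechanism data to ease the worry that a benefit over usual care might be non-specific. These scales therefore carry part of the design argument, although no SD, effect size or power is given for any of them.

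**Working it through.** **Inputs.** 75 per arm, 1:1 (Sections 9.2.2 and 6.3). Two-sided 0.05 for inferential tests (Section 9.4.1). *Assumed, because the documents do not give them:* the baseline-to-follow-up correlation r, the ratio k of follow-up SD to baseline SD, and, for power, a difference of 0.4 SD.

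**The plan's own figure.** The only stated power is for the primary endpoint: 83% for 45% versus 25% at two-sided 0.10. With pooled variance under the null:

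- null SE = √(2 × 0.35 × 0.65 / 75) = 0.0779
- alternative SE = √((0.45 × 0.55 + 0.25 × 0.75) / 75) = 0.0762
- power = Φ((0.20 − 1.645 × 0.0779) / 0.0762) = 82.7%

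The stated figure reproduces and does not depend on the point made here.

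**Equal SDs (k = 1).** Per unit of σ² and apart from the common factor 2/n:

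- variance of the difference in mean change: 2(1 − r)
- variance of the baseline-adjusted difference: 1 − r²
- ratio, adjusted to change: (1 − r²) / (2(1 − r)) = (1 + r)/2
- precision (1/variance) lost by using change: 1 − (1 + r)/2 = (1 − r)/2
- narrowing of the interval: 1 − √((1 + r)/2)

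| r | Variance ratio | Precision lost | Interval narrower by | 75 per arm is worth |
|---|---|---|---|---|
| 0.2 | 0.60 | 40% | 23% | 45 |
| 0.3 | 0.65 | 35% | 19% | 49 |
| 0.5 | 0.75 | 25% | 13% | 56 |
| 0.7 | 0.85 | 15% | 8% | 64 |
| 0.8 | 0.90 | 10% | 5% | 68 |
| 0.9 | 0.95 | 5% | 3% | 71 |

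**Unequal SDs.** The ratio becomes (1 − r²)k² / (k² + 1 − 2rk). Denominator minus numerator is 1 − 2rk + r²k² = (1 − rk)², which is never negative, so the ratio never exceeds 1. It reaches 1 when rk = 1. For example, at r = 0.7 and k = 1.4 it is 0.51 × 1.96 / (1.96 + 1 − 1.96) = 0.9996, and the gain disappears.

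**From means to ranks.** These formulas compare two mean-based analyses, whereas the plan uses ranks. Under normality the rank-sum test has asymptotic relative efficiency 3/π = 0.955, so the total loss would be 1 − 0.65 × 0.955 = 38% at r = 0.3 and 1 − 0.85 × 0.955 = 19% at r = 0.7.

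The planned test was also simulated directly against ANCOVA on baseline score (6,000 replicates, 75 per arm, two-sided 0.05, 0.4 SD difference). It was run once with normal scores and once with rounded scores held to 12–48 (mean 40, SD 6 before truncation) to imitate a ceiling.

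| r | Normal: rank-sum on change | Normal: ANCOVA | Ceiling: rank-sum on change | Ceiling: ANCOVA |
|---|---|---|---|---|
| 0.3 | 51% | 71% | 48% | 70% |
| 0.5 | 65% | 79% | 62% | 78% |
| 0.7 | 86% | 93% | 82% | 91% |

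With no true difference, both methods rejected in about 4.4% to 5.4% of replicates. The simulated variance ratios (ANCOVA to mean change) were 0.67, 0.76 and 0.86 for normal scores and 0.63, 0.71 and 0.83 with the ceiling, close to the formula.

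**The case against.** The best defence is that nothing here is an error. Randomisation protects a comparison of changes, and the simulated type I error was close to 5%. The outcomes are bounded Likert sums, one of them a two-item score from 2 to 10, and another is a single 0–100 item. A rank method is a reasonable choice for such data, and Section 9.4.1 allows for it. The endpoints are secondary and unpowered, in a single-site pilot with no decision rule attached to them, and the qualitative interviews also address mechanism.

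Most of that stands. It limits the point to efficiency and estimation. It does not remove the gain: ANCOVA kept its advantage on ceiling-limited scores, and the rank-sum test can stay beside it.

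A reader might infer more than the documents support:

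- *That the planned test is biased or invalid.* It is neither. Regression to the mean matters only conditionally on a chance baseline imbalance.
- *That this trial loses 15–35% of precision.* That range follows from r between 0.7 and 0.3 with equal SDs, and the documents give neither. It is also a statement about variance; interval width changes by about 8–19%.
- *That no intervals are planned.* Section 9.4.3.2 does plan 95% intervals for proportions and means. What it does not specify is an interval for the between-arm difference in change.
- *That every mechanism endpoint is affected.* CTM-15 has no baseline. Perceived Barriers has one, but Section 8.1 describes it as yes/no items without defining a total score, so it is left out here.

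**Conclusion.** The point holds as a free improvement. For ISEL-12, the Perceived Susceptibility subscales, IPQ-R Consequences and CASE-Cancer, the plan sets aside a baseline covariate that it already collects and specifies no adjusted between-arm difference.

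The direction of the gain does not depend on r or k: in large samples baseline adjustment is at least as precise as a mean-based change analysis. The size does depend on them, and it should be quoted only together with its assumptions. It is material at low to moderate r, small at r of 0.8 or more, and close to zero when rk is near 1. The power comparison rests further on an assumed 0.4 SD difference and complete questionnaires from 75 per arm.

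**What to change.** In Section 9.4.3.2, for these four measures:

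1. Make the main between-arm analysis an ANCOVA of the follow-up score on arm, baseline score, race and radiation facility, and report the adjusted mean difference with its 95% CI.
2. Name the follow-up visit. ISEL-12 and CASE-Cancer have only Visit 5. For Perceived Susceptibility and IPQ-R Consequences, name the last scheduled visit, Visit 4; the text does not now say which visit defines the change.
3. Keep the rank-sum test on change as a sensitivity analysis.
4. State that CTM-15 is compared as a post-baseline score. In the same paragraph, reconcile the list of pre/post constructs with Section 8.1: care coordination has no baseline measure, and no knowledge scale is defined.

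The cost is a wording change before the analysis. It needs no new data, visits or patients and leaves the primary analysis as it is.

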9.4.4 BASELINE DESCRIPTIVE STATISTICS

Baseline characteristics (e.g., demographics, oncologic details, behavioral characteristics) for the NDURE and Usual Care arms will be compared and descriptive statistics calculated. Baseline differences between the two groups, stratified by race and location of radiation facility, will be compared using t-tests and chi-square tests, or Wilcoxon rank sum and Fisher's exact tests as appropriate.

9.4.5 PLANNED INTERIM ANALYSES

N/A

9.4.6 SUB-GROUP ANALYSES

Planned sub-group analyses of the primary endpoint will occur based on age and sex to evaluate the impact of inclusion across the lifespan and sex as biologic variables. Historical data have not established an association between either age or sex with the primary endpoint⁶. Given the importance of race to the study objectives, analysis of the primary endpoint by race is evaluated as a secondary objective instead of planned subset analysis. Additional planned subset analyses will evaluate the impact of the NDURE intervention on the primary endpoint based on insurance status and fragmentation of care between the surgical facility and radiation facility, both of which have been described as risk factors for delayed PORT⁶. As such, both of these variables have the potential to confound the effect of the intervention were they to be imbalanced in a future RCT. As such, evaluating their impact on the primary endpoint in this study would allow for rational stratification in planned future RCTs.

9.4.7 TABULATION OF INDIVIDUAL PARTICIPANT DATA

Individual participant data will not be listed by measure and time point.

9.4.8 EXPLORATORY ANALYSES

N/A

10 SUPPORTING DOCUMENTATION AND OPERATIONAL CONSIDERATIONS

10.1 REGULATORY, ETHICAL, AND STUDY OVERSIGHT CONSIDERATIONS

10.1.1 INFORMED CONSENT PROCESS

We will obtain full written Informed consent from patients enrolling in the study. Informed consent will occur via face-face discussion between one of the study team members designated to perform informed consent and the potential study participant. After describing the study and allowing the potential participants to ask any questions, we will schedule interviews with those who are eligible and interested in participating in the study. Participant will have time to read the informed consent form and HIPAA document on their own. Consents will be written in simple, easy-to-understand language and obtained on the day of enrollment by the trained study coordinator. A study team member will answer any questions about the study and participants will be asked to sign the consent and HIPAA forms. All participants will sign informed consent forms before the interview. All participants will receive a copy of their informed consent and HIPAA forms for their records. The informed consent process will take place in a private room in the Rutledge Tower Head and Neck Cancer Clinic or in a private room in the HCC. Only the

study participant will provide informed consent. Subjects will be allowed up to one week to decide whether to participate in the study.

10.1.2 STUDY DISCONTINUATION AND CLOSURE

This study may be temporarily suspended or prematurely terminated if there is sufficient reasonable cause. Written notification, documenting the reason for study suspension or termination, will be provided by the suspending or terminating party to study participants, investigator, funding agency, and regulatory authorities. If the study is prematurely terminated or suspended, the PI will promptly inform study participants, the IRB, and sponsor/funding agency and will provide the reason(s) for the termination or suspension. Study participants will be contacted, as applicable, and be informed of changes to study visit schedule.

Circumstances that may warrant termination or suspension include, but are not limited to:

- Determination of unexpected, significant, or unacceptable risk to participants
- Insufficient compliance of study staff to the protocol (e.g. significant protocol violations)
- Data that are not sufficiently complete and/or evaluable

The study may resume once concerns about safety, protocol compliance, and data quality are addressed, and satisfy the funding agency, sponsor, IRB, Food and Drug Administration (FDA), or other relevant regulatory or oversight bodies (OHRP, DSMB).

10.1.3 CONFIDENTIALITY AND PRIVACY

Participant confidentiality and privacy is strictly held in trust by the participating investigators, their staff, the safety and oversight monitor(s), and the sponsor(s) and funding agency. This confidentiality is extended to the data being collected as part of this study. Data that could be used to identify a specific study participant will be held in strict confidence within the research team. No personally identifiable information from the study will be released to any unauthorized third party without prior written approval of the sponsor/funding agency. To help protect participant confidentiality, we will assign a unique study ID number to each subject's information in place of his/her name and will label data collection forms only with the ID number. All hard copy and electronic files will be stored appropriately using double-locked methods and password-protection. Only the study team member will have access to study records. Participant data will be collected and recorded on either a password-protected electronic data capture format (Research Electronic Data Capture; REDCap) or paper-based forms depending upon patient preference. For the paper collection data method, the data collection form will be labeled only with the participant's unique study ID number, and then stored within locked drawers in a locked office. The information on these paper forms will be transferred to a password-protected REDCap database such that all data will be stored in the password-protected REDCap Database. Only members of the study team will have access to the data. We have no plan to use laptops, jump drives, CDs/DVDs to transport data.

All research activities will be conducted in as private a setting as possible.

The study monitor, other authorized representatives of the sponsor or funding agency, representatives of the IRB, regulatory agencies or representatives from companies or organizations supplying the product, may inspect all documents and records required to be maintained by the investigator, including but not limited to, medical records (office, clinic, or hospital) and pharmacy records for the participants in this study. The clinical study site will permit access to such records.

The study participant's contact information will be securely stored at each clinical site for internal use during the study. At the end of the study, all records will continue to be kept in a secure location for as long a period as dictated by the reviewing IRB, Institutional policies, or sponsor/funding agency requirements.

It is NIH policy that the results and accomplishments of the activities that it funds should be made available to the public (see <https://grants.nih.gov/policy/sharing.htm>). The PI will ensure all mechanisms used to share data will include proper plans and safeguards for the protection of privacy, confidentiality, and security for data dissemination and reuse (e.g., all data will be thoroughly de-identified and will not be traceable to a specific study participant). Plans for archiving and long-term preservation of the data will be implemented, as appropriate.

To further protect the privacy of study participants, the Secretary, Health and Human Services (HHS), has issued a Certificate of Confidentiality (CoC) to all researchers engaged in biomedical, behavioral, clinical or other human subjects research funded wholly or in part by the federal government. Recipients of NIH funding for human subjects research are required to protect identifiable research information from forced disclosure per the terms of the NIH Policy (see <https://humansubjects.nih.gov/coc/index>). As set forth in 45 CFR Part 75.303(a) and NIHGPS Chapter 8.3, recipients conducting NIH-supported research covered by this Policy are required to establish and maintain effective internal controls (e.g., policies and procedures) that provide reasonable assurance that the award is managed in compliance with Federal statutes, regulations, and the terms and conditions of award. It is the NIH policy that investigators and others who have access to research records will not disclose identifying information except when the participant consents or in certain instances when federal, state, or local law or regulation requires disclosure. NIH expects investigators to inform research participants of the protections and the limits to protections provided by a Certificate issued by this Policy.

